Primary endpoint	Percentage change from baseline to Week 12 in sleep quality NRS	ITT	
 Discontinuation or interruption of study treatment due to Covid-19 pandemic, off-treatment data will be set as missing (hypothetical strategy). The assessments after patients resume treatment will be used. Discontinuation or interruption of study treatment not due to Covid-19 pandemic, all data collected following schedule after the treatment discontinuation will be used in the analysis (treatment policy strategy). Taking rescue medications ^b prior to Week 12: data will be set to missing values after the medication usage (hypothetical strategy) Taking prohibited medications ^b that affect sleep: All sleep related assessments (sleep NRS, SCORing subjective sleep loss scores, PROMIS sleep disturbance short form 8a individual question scores, ESS, actigraphy data) on that corresponding night will be set to missing (hypothetical strategy) Taking prohibited medications ^b that affect AD, data will be set to missing values after the medication usage (hypothetical strategy) 	A mixed effect model for repeated measures (MMRM) under the missing at random (MAR) framework will be used. The MMRM will include treatment, baseline value, randomization stratum, visits (up to week 12), treatment by visit interaction, and baseline sleep quality NRS by visit interaction terms all as fixed effects. Randomization stratum, treatment and visits will be considered as categorical parameters. No explicit imputation will be done for missing data.
Secondary objective: To evaluate the effect of dupilumab on objective and subjective quantitative sleep parameters, AD related outcomes, and daytime consequences of sleep deprivation.				

Endpoint Category (estimand)	Estimands			Population-level summary (Analysis and missing data handling)
	Endpoint(s) ^a	Population	Intercurrent event(s) handling strategy	
Secondary endpoint (treatment policy strategy/hypothetical strategy)	Change or percent change from baseline in Sleep and AD related outcomes	ITT	Same as the primary endpoint	The same MMRM with the baseline values corresponding to the outcome variables.

^a Additional key secondary endpoints are not included in this table but would be handled with a similar strategy as the endpoint type (ie continuous, binary, time-to-event) at other weeks. The key secondary endpoints are listed in [Section 8.2.23](#).

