8.2.23. Multiplicity issues

The overall type-I error rate will be controlled at the two-sided 0.05 level using a sequential testing procedure. In order for any secondary endpoints to be eligible for being declared significant, the primary endpoint must be significant at 0.05 significance level. The secondary endpoints will be tested following the hierarchical testing procedure with a pre-specified order, that is, inferential conclusions about successive secondary endpoints require statistical significance at 0.05 significance level of the previous one.

The following key secondary endpoints will be included in the multiplicity adjustment scheme and tested in the following order:

1. Percent change from baseline to Week 12 in peak pruritus NRS
2. Change from baseline to Week 12 in SCORAD total score
3. Change from baseline to Week 12 in SCORAD sleep VAS
4. Change from baseline to Week 12 in PROMIS Sleep Impairment SF8a score
5. Change from baseline to Week 12 in TST based on actigraphy data
6. Change from baseline to Week 12 in SE based on actigraphy data
7. Change from baseline to Week 12 in WASO based on actigraphy data
8. Change from baseline to Week 12 in SOL based on actigraphy data

Each endpoint will be tested at 0.05 (two-sided) level of significance. If at any step the null statistical hypothesis of no treatment difference is not rejected, the endpoints listed after that step will be reported at nominal level, otherwise will be technically eligible for being declared significant. Regardless of eligibility for being declared significant, all endpoints (non-key secondary and exploratory) will be tested at 0.05 (two-sided) level of significance and reported at nominal level.

9. Safety Analysis

All safety results will be summarized separately within the double-blind treatment period and the overall period (combined double-blind and OLE periods), using the Safety analysis set by actual treatment group and overall.

The observation periods include:

- The **pre-treatment** period is defined as the time from the signed informed consent date up to first administration of the IMP.
- The **randomized on-treatment** period is defined as the time from the first administration of the IMP (on Day 1) to the last administration of the IMP prior to Week 12 + 14 days if the patient does

not enter the OLE period, or until prior to the loading dose at Week 12 if the patient enters the OLE period.

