15.2. Schedule of Study Procedures

Study Procedure													
Visit (V)	Screening 1 ^g	Screening 2 ^g	Baseline V1	V2	V3	V4	V5	Primary End point Visit V6	V7	V8	End of Study/ Early discontinuation V9 ^h	UnSch Visit	Notes
Week (W)			W0	W1	W2	W4	W8	W12	W16	W20	W24		
Day (D)				D8	D15	D29	D57	D85	D113	D141	D169		
Visit window (±d)	D (-28 to -8)	D (-7 to -1)	D1	±3d	±3d	±3d	±3d	±3d	±3d	±3d	±3d		
Enrollment Screening/Baseline:													
Inclusion and exclusion criteria	X		X										
Informed consent	X												
Demography	X												
Concurrent illness	X		X										
IVRS call	X		X		X	X	X	X	X	X	X		
Study Treatment/Concomitant Medication:													
Study drug dispensation			X ^a		X ^b	X	X	X ^c	X	X			
Concomitant medications and procedures	X	X	X	X	X	X	X	X	X	X	X	X	
Efficacy:													
Physician Assessments:													

Study Procedure													
Visit (V)	Screening 1 ^g	Screening 2 ^g	Baseline V1	V2	V3	V4	V5	Primary End point Visit V6	V7	V8	End of Study/ Early discontinuation V9 ^h	UnSch Visit	Notes
Week (W)			W0	W1	W2	W4	W8	W12	W16	W20	W24		
Day (D)			D1	D8 ±3d	D15 ±3d	D29 ±3d	D57 ±3d	D85 ±3d	D113 ±3d	D141 ±3d	D169 ±3d		
Visit window (±d)	D (-28 to -8)	D (-7 to -1)											
IGA and BSA (for eligibility purpose only)	X		X										
EASI	X		X	X	X	X	X	X	X	X	X	X	
SCORAD	X		X	X	X	X	X	X	X	X	X	X	
Patient Assessments (Daily including week preceding baseline visit):													
Sleep Quality NRS ^d		X	X	X	X	X	X	X	X	X	X	X	
Sleep Diary ^d		X	X	X	X	X	X	X	X	X	X	X	
Peak pruritus NRS, Skin pain NRS, Skin sensitivity to touch, Skin burn NRS ^d		X	X	X	X	X	X	X	X	X	X	X	
Actigraphy ^d		X	X	X	X	X	X	X	X	X	X	X	
Patient Assessment (at clinic):													
PROMIS Sleep Related Impairment SF 8a			X	X	X	X	X	X	X	X	X	X	
Epworth Sleepiness Scale (ESS)			X			X		X			X	X	

Study Procedure													
Visit (V)	Screening 1 ^g	Screening 2 ^g	Baseline V1	V2	V3	V4	V5	Primary End point Visit V6	V7	V8	End of Study/ Early discontinuation v9 ^h	UnSch Visit	Notes
Week (W)			W0	W1	W2	W4	W8	W12	W16	W20	W24		
Day (D)			D1	D8	D15	D29	D57	D85	D113	D141	D169		
Visit window (±d)	D (-28 to -8)	D (-7 to -1)	D1	±3d	±3d	±3d	±3d	±3d	±3d	±3d	±3d		
POEM			X			X		X			X	X	
DLQI			X			X		X			X	X	
HADS			X			X		X			X	X	
ACQ-5, AR-VAS			X					X			X	X	
WPAI-AD			X			X	X	X			X	X	
Assess missed school/work days			X			X	X	X	X	X	X	X	
Center assisted Assessment:													
Psychomotor Vigilance Test (PVT)	X		X					X			X	X	

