15.3. Missing Efficacy Data

15.3.1. Handling of missing data and data whose interpretations have changed

The following will be applied to all efficacy endpoints:

- Patients will be encouraged to stay in the study if they discontinue the IMP, even due to Covid-19 pandemic (IcEv1 and IcEv2).
 - If discontinuation or interruption of study treatment due to Covid-19, off-treatment data will be set to missing. The assessments after patients resume treatment will be used.
 - If discontinuation or interruption of study treatment not due to Covid-19, all data collected following schedule after the treatment discontinuation will be used in the analysis.
- Taking selected prohibited medications that affect sleep (Protocol Section 6.5.1), all sleep related assessments (sleep quality NRS, SCORAD sleep VAS and total score, PROMIS sleep impairment SF8a total score, ESS, and actigraphy data) on that corresponding night will be set to missing. AD assessments will be included in the analyses.
- Taking selected prohibited medications that affect AD (Protocol Section 6.5.1), all AD assessments will be set to missing after the medication usage.
- Taking rescue medications for AD (ie. to control intolerable AD symptoms) is allowed. For the purpose of efficacy analysis, all AD assessments will be set to missing after the medication usage.
- If a patient discontinues from treatment or from the study, or is taking rescue or selected prohibited medications, the patient will be counted as a non-responder for the time points after discontinuation or rescue/prohibited medication start for all binary endpoints.

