15.8. Patient-Reported Outcomes (PROS)

Patient oriented eczema measure (POEM)

The POEM is a 7-item, validated questionnaire used in clinical practice and clinical trials to assess frequency of disease symptoms in children and adults (9). The format is a response to 7 items (dryness, itching, flaking, cracking, sleep loss, bleeding, and weeping) based on frequency during the past week (ie, 0 = no days, 1 = 1 to 2 days, 2 = 3 to 4 days, 3 = 5 to 6 days, and 4 = all days) with a scoring system of 0 to 28; the total score reflects disease-related severity.

POEM score will be directly provided by KONEKSA.

PROMIS Sleep Related Impairment Short Form 8a

The PROMIS is a DSM-5, Level 2, sleep disturbance measure. This study uses the 8-item PROMIS Sleep Related Impairment Short Form that assesses the domain of sleep related impairment in the past 7 days in individuals age 18 and older.

Each item asks the patient to rate the severity of the patient’s sleep related impairment during the past 7 days. Each item on the measure is rated on a 5-point scale (1 = not at all; 2 = a little bit; 3 = somewhat; 4 = quite a bit; and 5 = very much) with a range in score from 8 to 40 with higher scores indicating greater severity of sleep impairment.

Locate the applicable score conversion in [Table 15.8.1](#), and use this table to translate the total raw score or imputed total score into a PROMIS T-score for each participant. The T-score rescales the raw score into a standardized score with a mean of 50 and a standard deviation of 10. Therefore, a person with a T-score of 40 is one SD below the mean. The standardized T-score is reported as the final score for each participant.

Table 15.8.1 PROMIS Sleep-Related Impairment conversion table

Raw Score	T-score	Raw Score	T-score
8	30	25	60.3
9	35.1	26	61.3
10	38.7	27	62.3
11	41.4	28	63.3
12	43.6	29	64.3
13	45.5	30	65.3
14	47.3	31	66.3
15	48.9	32	67.3
16	50.3	33	68.4
17	51.6	34	68.5
18	52.9	35	70.7
19	54	36	71.9
20	55.1	37	73.3
21	56.1	38	75
22	57.2	39	76.9
23	58.2	40	80
24	59.3		

PROMIS score will be directly provided by KONEKSA.

Epworth Sleepiness Scale (ESS)

The ESS is a self-administered questionnaire with 8 questions. Respondents are asked to rate, on a 4-point scale (0-3), their usual chances of dozing off or falling asleep while engaged in eight different activities. Most people engage in those activities at least occasionally, although not necessarily every

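### The SAP's one-night deletion rule does not fit PROMIS, a 7-day recall scale completed at clinic visits; separately, the T-score table has an apparent misprint at raw score 34

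*SAP*

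**What the plan says.** **Deletion rule.** For prohibited medications that affect sleep, SAP 15.3.1 lists the sleep assessments to be removed, ending with "PROMIS sleep impairment SF8a total score, ESS, and actigraphy data) on that corresponding night will be set to missing". The estimand table (SAP Table 3.1.2) labels this a hypothetical strategy, but its list ends with "PROMIS sleep disturbance short form 8a individual question scores, ESS, actigraphy data) on that corresponding night will be set to missing". Neither place gives a separate window for PROMIS.

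**Instrument.** SAP 15.8 describes PROMIS as a form "that assesses the domain of sleep related impairment in the past 7 days in individuals age 18 and older". The schedule in SAP 15.2 lists it under a heading that begins "Patient Assessment (at clinic", at Weeks 0, 1, 2, 4, 8, 12, 16, 20 and 24.

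**Scoring.** SAP 15.3.2 defines the PROMIS total as the sum of the eight items. SAP 15.8 then tells the analyst to "use this table to translate the total raw score or imputed total score into a PROMIS T-score for each participant" and makes the T-score the final reported score. It adds that the data vendor will supply the PROMIS score. SAP 8.2.10 models the raw score and the T-score.

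**Testing.** In SAP 8.2.23 the fourth key secondary endpoint is "Change from baseline to Week 12 in PROMIS Sleep Impairment SF8a score". The sequence runs at the two-sided 0.05 level, and the four actigraphy endpoints (TST, SE, WASO, SOL) follow PROMIS.

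**The concern.** A rule that removes one night's data suits a measure taken nightly, such as the sleep quality NRS or actigraphy. A PROMIS score summarises a week. If a sleep-affecting medication was taken on a night of that week that is not the one counted, the score stays in, although the stated strategy is to set aside outcomes affected by such use. The SAP gives no window, so whoever programs the analysis has to choose one.

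ESS is in the same sentence. It asks about the usual chance of dozing and has no night attached. The SCORAD sleep VAS is also listed, and neither document's text states the period it covers.

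The T-score table raises a smaller, separate question. One entry is out of line with its neighbours in a table that the SAP tells the analyst to use.

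PROMIS carries some weight in the testing. If its null hypothesis is not rejected, all four actigraphy endpoints are reported at nominal level only. The primary endpoint is a nightly measure and is not affected by either fault.

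**Working it through.** **1. Night rule**

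Inputs:
- PROMIS recall: 7 nights (SAP 15.8).
- Nights counted by the rule: 1 (SAP 15.3.1 and Table 3.1.2). I take this as a single night tied to the visit; the text does not define it for a 7-day scale.
- Nights of use in the recall week: k, placed at random (assumption; neither document gives a rate or pattern of use).

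Chance that the counted night is a night of use = k/7. Share of affected scores kept = 1 − k/7.

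| k | removed | kept |
|---|---|---|
| 1 | 0.143 | 0.857 |
| 2 | 0.286 | 0.714 |
| 3 | 0.429 | 0.571 |
| 6 | 0.857 | 0.143 |
| 7 | 1.000 | 0.000 |

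These shares are conditional on use. They do not say how many Week 12 scores are affected.

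**2. The two statements of the rule, side by side**

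- SAP 15.3.1 names the sleep impairment form and deletes its total score.
- Table 3.1.2 names a sleep disturbance form and deletes individual question scores.
- SAP 15.3.1 also deletes the SCORAD total score. Table 3.1.2 lists only the SCORAD sleep loss scores.

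**3. Table 15.8.1**

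The printed figure at raw 34 is 68.5. It is not reproduced by the table's own sequence:

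| raw | T-score | step from previous |
|---|---|---|
| 32 | 67.3 | 1.0 |
| 33 | 68.4 | 1.1 |
| 34 | 68.5 | 0.1 |
| 35 | 70.7 | 2.2 |
| 36 | 71.9 | 1.2 |

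Every other step from raw 20 to raw 37 lies between 1.0 and 1.4. Three estimates of the entry from the rest of the table:
- Midpoint of the neighbours: (68.4 + 70.7)/2 = 69.55, so the residual is 68.5 − 69.55 = −1.05. For raw 12 to 38 the same residual is at most 0.15 in size, apart from raw 33 and 35 (0.5 each), which are disturbed by the same entry.
- Cubic through raw 32, 33, 35 and 36: (−67.3 + 4×68.4 + 4×70.7 − 71.9)/6 = 69.53.
- Polynomials of degree 2 to 4 over raw 28 to 39, leaving out 34: 69.43 to 69.50.

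A value of 69.5 would give steps of 1.1 and 1.2.

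Effect on an arm's mean T-score at a visit = share scoring 34 × 1.05. The documents do not give the share, so I use an assumed range. With normal raw scores of mean m and SD s, the share is Φ((34.5 − m)/s) − Φ((33.5 − m)/s):
- m = 24, s = 7: 2.1%, a shift of 0.021 × 1.05 = 0.022.
- m = 30, s = 6: 5.3%, a shift of 0.053 × 1.05 = 0.056.

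Over a wider range of 1% to 10% the shift is 0.011 to 0.105 T-points, at most about 0.01 SD on a scale whose SD is 10.

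**The case against.** **The rule is ambiguous, not plainly wrong.** The SAP does not define the corresponding night for PROMIS, and a sensible programmer might apply it to the whole recall week. This stands in part: the retained shares hold only under the literal reading. But no text supports the wider reading, and a pre-specified strategy should not depend on it.

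**The shares of 57% to 86% are the unfavourable cases.** The prohibited list includes sedative antihistamines taken more than 5 days per week. At 6 or 7 nights of use the same formula keeps only 14% or none. Regular users of sedative anxiolytics or hypnotics are also excluded at entry, and these drugs are prohibited on study. This stands, and the number of affected scores may be small. Low weekly use is still plausible, since exclusion criterion E14 admits patients with occasional use of up to twice a week before the last 2 weeks.

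**Direction.** A reader might infer that sedatives improve the retained scores and that heavier use on placebo shrinks the treatment difference. The documents do not support that. They give no use by arm, and a sedative could improve or worsen a score of sleep-related impairment.

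**The table entry.** A reader might infer that it corrupts the fourth key test or mis-scores every visit at raw 34. Neither is established. The endpoint is the total score, which SAP 15.3.2 defines as the raw sum, and the vendor may supply converted scores without using the printed table. SAP 8.2.23 says only score and SAP 15.8 calls the T-score final, so the question is open.

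**One dose would discard a week's score.** True. That is the price of applying the stated hypothetical strategy to a 7-day instrument.

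**Conclusion.** Both faults are in the text and should be corrected; the night rule matters more.

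As written, the rule for sleep-affecting prohibited medication does not deliver the hypothetical strategy for PROMIS. Under the literal one-night reading, with use on 1 to 3 random nights, 86% to 57% of affected scores remain. The documents give neither the frequency of use nor the direction of any bias, so no effect on the PROMIS test, or on the actigraphy endpoints behind it, has been shown. The same sentence misfits ESS, an exploratory endpoint, and the two statements of the rule need to agree.

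The raw 34 entry is about 1 T-point too low by the table's own sequence. The official value is not in the documents, so about 69.5 is an inference. The entry bears on the T-score analysis in SAP 8.2.10 if the printed table is used, and on the fourth key test only if that test uses the T-score. Its effect on means is small: about 0.1 T-points at most under the assumed shares.

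**What to change.** - In SAP 15.3.1 and Table 3.1.2, match the exclusion window to each instrument's recall. Set PROMIS to missing if a sleep-affecting prohibited medication was used on any night of its 7-day recall. State a window for ESS and for the SCORAD sleep VAS. Keep the one-night rule for the sleep quality NRS and actigraphy.
- Use the same PROMIS form name and score level in both places, and the same SCORAD components.
- Check raw 34 in Table 15.8.1 against the source conversion table, correct it, and confirm that the vendor's conversion uses the corrected value.
- State in SAP 8.2.23 whether the raw total or the T-score is tested.

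The cost is a few sentences, one table entry and one query to the vendor. The downside is a few more missing PROMIS scores, which the planned MMRM handles under its missing-at-random assumption.

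### After rescue or AD-active prohibited medication, SAP Table 3.1.2 removes the sleep endpoints, including the primary, while SAP 15.3.1 as written keeps them

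*SAP*

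**What the plan says.** **SAP Table 3.1.2.** The primary row has one endpoint, percent change to Week 12 in sleep quality NRS. For rescue medication its rule reads "prior to Week 12: data will be set to missing values after the medication usage (hypothetical strategy"). For prohibited medication the rule reads "that affect AD, data will be set to missing values after the medication usage (hypothetical strategy"). Since the row has no other endpoint, the data in question are the sleep quality NRS scores. The secondary row covers change or percent change in sleep and AD outcomes, and its handling is "Same as the primary endpoint".

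**SAP 15.3.1.** This section opens with "The following will be applied to all efficacy endpoints". For rescue it says "For the purpose of efficacy analysis, all AD assessments will be set to missing after the medication usage", and the bullet on AD-active prohibited medication likewise removes only AD assessments. The bullet on sleep-active prohibited medication defines the other class: "all sleep related assessments (sleep quality NRS, SCORAD sleep VAS and total score, PROMIS sleep impairment SF8a total score, ESS, and actigraphy data"). It removes these for the night concerned and keeps AD assessments in the analysis. Binary endpoints have their own non-responder rule in the same section.

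**The concern.** The two texts give opposite instructions for the primary endpoint after the same event. Table 3.1.2 removes a sleep quality NRS score recorded after rescue. SAP 15.3.1 files that score under sleep, removes only AD assessments, and so keeps it.

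SAP 15.3.1 is the section on handling missing and altered data, so a programmer could reasonably build the analysis dataset from it. The MMRM would then mix scores under study treatment with scores under rescue, and its Week 12 contrast would not be the hypothetical estimand in Table 3.1.2. The choice between the two rules should not be left open until after unblinding. The same split affects most of the endpoints in the testing sequence.

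**Working it through.** **1. Can the texts be reconciled?**

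| Event | Table 3.1.2, primary row | SAP 15.3.1 |
|---|---|---|
| Rescue before Week 12 | sleep quality NRS removed | AD assessments removed |
| AD-active prohibited medication | sleep quality NRS removed | AD assessments removed |
| Sleep-active prohibited medication | sleep assessments removed for that night | sleep assessments removed for that night; AD assessments kept |

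The texts would agree if AD assessments included sleep quality NRS. The last row rules this out, because 15.3.1 removes one class and keeps the other. The SAP defines the term nowhere. Its lists of AD variables in 6.2.2 and 8.2.22 serve other purposes, and neither contains sleep quality NRS.

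**2. Endpoints reached.** SAP 8.2.23 tests the primary and then 8 key secondary endpoints.
- Peak pruritus NRS is an AD measure, so both texts remove it: no conflict.
- SCORAD sleep VAS, PROMIS, and actigraphy TST, SE, WASO and SOL are sleep related in 15.3.1: 6 in conflict.
- SCORAD total is sleep related in 15.3.1 but an AD measure in 6.2.2 and 8.2.22. The sleep list in Table 3.1.2 omits it: "SCORing subjective sleep loss scores, PROMIS sleep disturbance short form 8a individual question scores, ESS, actigraphy data". Read as sleep related only, it makes 7.

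The reach is the primary plus 6 of 8, or plus 7 of 8.

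**3. The plan's own power (SAP 4.1).** Inputs: 50 placebo and 100 dupilumab patients, SD 44, difference 25, two-sided alpha 0.05. SE = 44 × √(1/50 + 1/100) = 7.62. Power is 90.7% by normal approximation and 90.3% by t-test with 148 df. The stated 90% reproduces.

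**4. Shrinkage if post-rescue scores are kept.** The documents give no rescue rate and no sleep benefit of rescue, so both are assumed. Shrinkage = (placebo rescue rate − dupilumab rescue rate) × benefit in rescued patients.
- 0.05 × 15 = 0.75 points
- 0.05 × 30 = 1.5 points
- 0.10 × 15 = 1.5 points
- 0.10 × 30 = 3.0 points
- Equal rates: 0

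This is 0.75/7.62 = 0.10 to 3.0/7.62 = 0.39 of the standard error. The 30-point benefit is an outer bound, since it exceeds the planned drug effect of 25.

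**5. Power under each rule.** Keeping holds n at 50 and 100 and lowers the difference. Deleting holds the difference at 25 and drops rescued patients at Week 12. The t-test and SD 44 are used throughout.

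| Assumed rescue, placebo v dupilumab | Delete (Table 3.1.2) | Keep, 15-point benefit | Keep, 30-point benefit |
|---|---|---|---|
| 10% v 5% | n 45 and 95, SE 7.96: 87.7% | difference 24.25: 88.5% | difference 23.5: 86.5% |
| 20% v 10% | n 40 and 90, SE 8.36: 84.3% | difference 23.5: 86.5% | difference 22: 81.8% |

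The deletion figures are lower bounds, because the MMRM recovers some information from earlier visits. Within this range either rule can have the higher power.

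**The case against.** **The governing text can largely be identified.** Table 3.1.2 is the estimand table. SAP 13 says intercurrent events were added for the primary and key secondary endpoints, and the summary in SAP 15.1 marks estimands for those same endpoints. The conflicting text is in an appendix. This makes the intention fairly clear, and it stands as far as it goes. But no sentence gives the table precedence, and 15.3.1 claims all efficacy endpoints. The statement in SAP 8 that all efficacy measurements are considered, including those after stopping study drug, does not mention rescue and does not settle the matter.

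**A reader might infer that following 15.3.1 costs power.** The documents do not support this. The 90% figure assumes 150 evaluable patients and makes no allowance for rescue. The proper comparator is deletion under Table 3.1.2, which also loses power, and the comparison can go either way.

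**A reader might infer that Table 3.1.2 contradicts itself.** For discontinuation not due to Covid-19 it says "all data collected following schedule after the treatment discontinuation will be used in the analysis (treatment policy strategy"), while SAP 15.11 and Protocol 6.5.3 link systemic rescue to stopping study drug. But SAP Table 4.5.1 defines discontinuation and rescue as separate intercurrent events, each with its own strategy. A workable reading is that discontinuation alone leaves the data in and rescue takes them out. One clarifying sentence is enough.

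**A reader might lead with SCORAD total as an affected endpoint.** SAP 6.2.2 and 8.2.22 treat it as an AD measure, so 6 key secondary endpoints is the better-supported count.

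**Conclusion.** The conflict is real and the SAP should be corrected. Following 15.3.1 as written keeps post-rescue sleep quality NRS in the primary analysis, contrary to the hypothetical strategy in Table 3.1.2. It does the same for 6 of the 8 key secondary endpoints, or 7 on the narrower reading of SCORAD total.

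This conclusion rests on the text and does not depend on the arithmetic. The size cannot be known from the documents. If placebo patients are rescued more often and rescue helps sleep, keeping the scores pulls the estimated difference towards zero, by about 0.75 to 3 of the planned 25 points on the assumed inputs. That direction is conservative for dupilumab, so the documents give no ground for inferring a false positive from it. With equal rescue rates the shift is about 0. No net power loss is claimed.

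**What to change.** Before the Week 12 database lock and unblinding:

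1. Amend the two 15.3.1 bullets on rescue and AD-active prohibited medication to match Table 3.1.2, with all continuous primary and secondary endpoints made missing after the event. List them by name: sleep quality NRS, peak pruritus NRS, SCORAD total, SCORAD sleep VAS, PROMIS SF8a, POEM, DLQI, and actigraphy SE, TST, WASO and SOL. The non-responder rule for binary endpoints can stay.
2. State that Table 3.1.2 prevails for the primary and all continuous secondary endpoints. Limiting precedence to the key secondary endpoints would be narrower than the table's own secondary row.
3. Name the rule for the exploratory endpoints, in particular ESS and the sleep diary measures, which the 15.3.1 sleep list omits.
4. As a clarification, add one sentence saying which data-handling rule applies when rescue and treatment discontinuation coincide.

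The cost is SAP wording only: no new data and no extra model run. SAP 1 already commits to making any changes before database lock. The change concerns analysis data handling and leaves the clinical use of rescue untouched.
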